### 3 BACKGROUND AND RATIONALE

Symptoms of existential distress in patients with life-threatening cancer diagnoses are common, difficult to meaningfully treat, and cause extensive suffering at the end of life. Rates of existential distress in this population in general are estimated to be as high as 25% to 50%. Existential distress, along with associated symptoms of anxiety and depression, have been shown to predict poor longitudinal outcomes, reduced quality of life (QoL), higher utilization of opioid analgesics, and care-provider burnout. There is evidence to suggest that existential distress- as measured by validated tools- is a distinguishable phenomenon from other current recognized DSM diagnoses such as depressive and anxiety disorders.

In patients with cancers of the GI tract, surgery is essential for curative intent. In patients for whom curative surgical resection is not an option, whether due to distant metastatic spread, local tumor invasion or patient comorbidities, the absence of curative options further contributes to the development of existential distress, potentially leading to decreased QoL, higher pain scores and even shorter survival. In patients with advanced non-small-cell lung cancer, several previous reports have suggested that early palliative intervention may increase overall survival and/or QoL. This may be partially mediated by resources that address aspects of existential distress.

Current treatments for existential distress in this population are limited. Usually, sedative medications are utilized initially to control symptoms, primarily GABA agonist medications. In severe cases patients are rendered minimally conscious utilizing intravenous infusions of medications such as propofol or phenobarbital. This is referred to as *terminal sedation* (Rousseau, 2001). These interventions serve to lessen individual distress, but come at a cost of diminished awareness and limited meaningful interaction with family and friends at end of life.

A variety of types of therapy are utilized in addition to medications, most of which seek to normalize and validate the symptoms, whether as an individual or group. Multiple other options, such as dignity therapy, seek to help elucidate the legacy that will be left after the patient's death (Vuksanovic et al., 2017). These therapies have been shown to be effective (Cuevas et al., 2021) but the availability of experienced practitioners, short duration of effect and duration of therapy (8 weeks) limits the utility in those with severe symptoms or limited life expectancy. Given advances in medical therapies, the number of people living with terminal illnesses is increasing (Etkind et al., 2017). Additional therapies will be necessary to deal with the increasing burden of mental health issues that will invariably accompany this rise.

### 3.1 Ketamine

Ketamine, one of the most used anesthetic medications in the world and one of the World Health Organization's essential medications, is a dissociative anesthetic that exerts pharmacological actions through antagonism at the NMDA receptor, altering glutamatergic tone in the brain (Zorumski et al., 2016). Intranasal ketamine in the form of Spravato, or the s-enantiomer of racemic ketamine, recently received FDA approval for the treatment of depression, and multiple trials have shown the effectiveness of intravenous ketamine infusions for acute depression and suicidality (Abbar et al., 2022; Andrade, 2017; Ekstrand et al., 2022; Fava et al., 2020; Mandal et al., 2019; Singh et al., 2016).

There is evidence that ketamine infusions can have a beneficial effect on mental health disorders without associated psychotherapy, including for the treatment of major depressive disorder. Ketamine-assisted psychotherapy (KAP) delivers this treatment in the context of a psychotherapeutic process and seems to increase the positive benefits of this intervention, by modulating the self-awareness and self-referential processing of the participant and potentially prolonging therapeutic effect (Bottemanne et al., 2022; Dore et al., 2019; Krupitsky & Grinenko, 1997; Mathai et al., 2022). There is a strong reason to believe that this aberrant self-referential processing plays a part in existential distress. Currently there is limited literature regarding the use of ketamine and existential distress, but initial case reports point to the need for larger more focused studies to ascertain benefits. In a case series and an open label-trial, oral ketamine was found to be a rapid, safe, and tolerable treatment for depression in patients receiving hospice care (S. A. Irwin & Iglewicz, 2010; Stefanczyk-Sapieha et al., 2008). Ketamine's anti-nociceptive properties also suggest it may be an effective treatment for patients often dealing with intractable pain symptoms (Castellanos et al., 2020)

Ketamine has a favorable pharmacological profile as it relates to drug interactions, side effects, and time to therapeutic response. It is used in the adult and pediatric population as an anesthetic and analgesic in surgery, acute care, and trauma and pain management. It has been used in management of chronic pain in hospice and palliative care populations for breakthrough and chronic pain. IM Ketamine has a 90-95% bioavailability, has a short half-life, and it does not depress the respiratory drive. Many of those suffering from existential distress are currently taking at least one SSRI, SNRI or MAOI anti-depressant, which may take 4-6 weeks to full therapeutic response and relief of symptoms, time which a population of patients with limited life expectancy lacks. Ketamine's antidepressant effects can be observed and measured within hours to days of administration.

This study will contribute to the knowledge base around the use ketamine as a medicine used in alleviating emotional suffering at the end of life. There are currently limited tools for this condition. This study will inform a larger randomized controlled trial.

### 3.2 Patient Population Background

Patients with advanced cancers of the GI tract often have limited treatment options and poor prognosis. These cancers can originate from a wide variety of sources and include hepatic, biliary, pancreatic, small bowel, colon and rectal cancers.

Treatment modalities such as chemotherapy, immunotherapy or surgical resection often carry significant morbidity. Patients for whom curative surgical resection is not an option, whether due to distant metastatic spread, local tumor invasion or patient co-morbidities, may have significant physical symptoms as well as concomitant existential distress.

Existential distress is distress that originates from complexities and contradictions within one's lived experience and relationship to the world around them. It occurs when meaning and value become "unclear" (Lo 2018). Existential distress appears to be a distinguishable phenomenon from other current recognized DSM diagnoses such as depressive and anxiety disorders.

Symptoms of existential distress in patients with life-threatening cancer diagnoses are common, difficult to meaningfully treat, and cause extensive suffering at the end of life. Rates of existential distress patients with advanced cancer are estimated to be as high as 25% to 50% (Grassi 2017).

Existential distress, along with associated symptoms of anxiety and depression, have been shown to predict poor longitudinal outcomes, reduced quality of life, higher utilization of opioid analgesics, and care-provider burnout.

### **3.3 Storyline Health Assessments**

#### **3.3.1 Overview**

Storyline is a flexible research platform that will be used to deliver assessments during the course of the study. Storyline extracts features from video, audio, and natural language and overlays it with other data sources like patient records, genome data and outcomes.

Participants are owners of their data and can access it at any time, and even delete it. However, the study will not be able to provide direct meaningful interpretations for participants. Note, that participants may be able to choose some non-research interactions within the Storyline app, such as what celebrities they look like. This is not considered a benefit nor will be included in the research data, it's for entertainment purposes for the participants.

#### **3.3.2 Storyline Core Questions of Health**

The baseline assessment is designed to mimic a typical clinical psychiatric diagnostic interview and a neurological assessment. The psychiatric portion is a 60- minute program broken into six different 10-minute assessment sessions. The neurological portion is a 10-mintute assessment.

Patients will be notified through the Storyline app on their smartphone or smart device to complete the various study assessments. Storyline manages reminders and makes the process simple.

The objective is to create an effective and fast algorithm for feature selection and question selection to build assessments, diagnostic biobehavioral markers and predictive models from Storyline captured speech, vocal and facial data. The proposed algorithm has 3 components, including (1) rapid feature and question filtering based on variance, (2) feature selection using a method that integrates mutual information and random forest importance scores and (3) question selection using a deep learning method that ranks the predictive value of each question using the optimized features. The steps are as follows:

**Rapid Question Filtering** – The first step in the Short Story algorithm will be to filter questions, assessments and A.I. features in the storyARC and storyTIME files that have little information content. To do this, we will compute the variance for each measured feature for each question in the data for all people in a customer's pilot study. The variance is scaled to account for differences in units. We then sum the variance for each feature for each question, apply a min-max absolute scale for interpretation that scores questions from 0 (low information content) to 100 (high information content). The results will enable users to rapidly screen, rank and prune questions with little to no information content by pruning the bottom 25% of tested candidate questions.

**Feature Selection:** Storyline AI measures over 20,000 speech, vocal and facial features from the responses for each question and many are correlated or not useful for detecting some phenotypes of interest. Therefore, in this second step, Short Story technology performs a feature selection analysis that uncovers the most useful features for each tested question in an assessment for predicting a particular phenotype or outcome. The major objective is to uncover the best questions and features when the available data has limited sample size and classes are imbalanced. Our approach will involve implementing the qualitative mutual information (QMI) feature selection algorithm previously detailed by others and proven for high dimensional data, including microarray data for tens of thousands of genes (Nagpal and Singh, 2019). The algorithm will provide a score that combines random forest (RF) feature importance scores with mutual information to obtain a QMI value for each feature. QMI is more powerful than random forest (RF) importance or mutual information alone for feature selection, as previously described (Nagpal and Singh, 2018). In brief, RF will be applied to the speech, vocal and facial feature sets separately for each question and the importance scores of each feature will be calculated, as well as mutual information. RF importance scores will be converted to Preference scores and multiplied by the mutual information to define QMI values for each feature. The features will then be ranked by QMI values and features with a  $QMI > 0$  will be retained. The results will return the most useful speech, facial and vocal features for each question. The usefulness of the features is determined from their ability to differentiate the two classes in a study, such as control versus sick patients.

This approach has many advantages, including broad utility with few parameters to tune, applications to diverse data types with few samples and acceptable computational speed. RF importance scores are powerful for ranking correlated features. Mutual information, which determines the amount of information one random variable can provide about another variable, is then incorporated to further help remove irrelevant and redundant features. When accounting for accuracy and computational efficiency, this combined approach outperforms most methods, including filter, wrapper, embedded and hybrid feature selection strategies (Nagpal and Singh, 2019).

**Question Selection:** The final step of the Short Story algorithm will provide a score that determines the individual questions that should be retained in a new assessment and those that can be eliminated. In this approach, the input is all of the candidate questions and their optimized speech, vocal and facial features revealed from Short Story Score #2. The individual questions and question combinations that show the most value for predicting the classes of interest will then be determined. We will create a simple two-layer neural network that is architected to take Storyline speech, vocal and facial features as inputs to predict the

phenotypic classes of interest. The algorithm will be designed such that questions are tested in all possible pairwise combinations with 5-fold cross validation. The mean accuracy for predicting the target phenotype is determined for each question combination. Each pairwise question combination is then assigned an index. To compute the Short Story score for each question, we multiply the index and the mean classification accuracy for all question pairings in which that question was included in the predictive model. This vector of index\*accuracy values is summed to yield a score and then the scores for all of the candidate questions are min-max scaled to create the final Short Story question ranking score from 0-to-100, where a high score indicates important questions, and a low score indicates questions that can be pruned. The final results will return the ranking for each question and the mean classification accuracy values for each question.

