#### 2.3.3 To assess the effect that KAP has on symptoms of existential distress and depression in patients with non-operable GI cancers as measured by the Spiritual Well-Being (FACIT-Sp)

Exploratory Endpoint: Mean change in score on FACIT-Sp from baseline to Day 30 post completion of intervention.

**2.3.4** To develop an algorithm with Storyline Health technology to rapidly discover the most predictive and information rich components in the assessment of existential distress and its treatment response.

Exploratory Endpoint: Identification of a behavioral phenotype that better predicts a response to ketamine intervention.

**2.3.5** To evaluate the completion rate of questionnaires using the Storyline platform.

Exploratory Endpoint: The percentage of questionnaires completed.

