## 9 STATISTICAL CONSIDERATIONS

### 9.1 Sample size determination

This is a descriptive study. The planned sample size is 12 enrolled subjects. For the study to be a success, at least 9 of 12 subjects must be consented, enrolled and complete the study. If at least 9 of 12 subjects complete the study, the lower bound of the 95% exact binomial confidence interval for the completion rate will exceed of 34%.

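### The Storyline rule that retains every feature with QMI > 0 is not calibrated to chance: with 12 patients, pure noise leaves roughly 225 to 2,430 retained features per question, and the later cross-validation does not correct this

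*Combined protocol and SAP*

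**What the plan says.** Section 3.3.2 describes three steps: a variance filter on questions, feature selection, and question selection.

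- Size of the problem: "Storyline AI measures over 20,000 speech, vocal and facial features from the responses for each question". Section 9.1 adds: "The planned sample size is 12 enrolled subjects".
- Score: "RF will be applied to the speech, vocal and facial feature sets separately for each question", and then "RF importance scores will be converted to Preference scores and multiplied by the mutual information to define QMI values for each feature".
- Retention: "The features will then be ranked by QMI values and features with a" QMI above zero are retained and returned as the most useful ones for that question.
- Target: "The usefulness of the features is determined from their ability to differentiate the two classes in a study, such as control versus sick patients".
- Next step: the selected features enter a two-layer neural network. Question pairs are compared by 5-fold cross-validation, and questions receive a score min-max scaled from 0 to 100, together with mean accuracies.

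The endpoint served, under 2.3.4, is: "Identification of a behavioral phenotype that better predicts a response to ketamine intervention". Section 9.5 makes its analysis descriptive. Neither section says when a phenotype counts as identified, and 3.3.2 gives no chance reference for the cut-off.

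**The concern.** A cut-off of zero would work as a screen only if an uninformative feature tended to score zero or below. Plug-in mutual information cannot be negative. Impurity-based forest importance is positive for any feature that gave a useful split in any tree. With 12 patients and more than 20,000 candidates, trees readily find features that split the classes by chance. The number retained then depends on how many trees are grown rather than on how much information the features carry.

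At stake is the meaning of the 2.3.4 output. The procedure would present noise as useful features and use it to rank questions for keeping or pruning in a new assessment. Nothing in the plan would let a reader tell this from a real finding.

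**Working it through.** The documents give no count of retained features and no accuracy target, so there is no figure of the plan's own to reproduce. The check is a simulation of pure noise.

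**Inputs from the documents.** 12 patients (9.1); 20,000 features per question, forests run separately on three feature sets, two classes, retention at QMI > 0 (all 3.3.2).

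**Assumptions, because the plan is silent.** On tuning, 3.3.2 says only: "This approach has many advantages, including broad utility with few parameters to tune". Assumed: three sets of about 6,667 features; 100, 500 or 1,000 trees per forest; √p features tried per split; Gini importance; Preference score proportional to importance; mutual information (MI) from 2 bins, 3 bins or 3 nearest neighbours; class splits 6/6, 4/8 and 3/9; independent features.

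**Step 1: chance separation.** A noise feature separates classes of size k and 12 − k perfectly with probability 2/C(12, k). The expected number among 20,000 is:
- 6/6: 20,000 × 2/924 = 43
- 4/8: 20,000 × 2/495 = 81
- 3/9: 20,000 × 2/220 = 182

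**Step 2: noise features retained per question, three forests.**

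| Trees per forest | Importance > 0 | Importance > 0 and MI > 0 |
|---|---|---|
| 100 | 290–320 | 225–300 |
| 500 | 1,310–1,410 | 980–1,370 |
| 1,000 | 2,340–2,490 | 1,960–2,430 |

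The low ends of the last column at 100 and 500 trees come from nearest-neighbour MI, run at 6/6 only; it was not run at 1,000 trees. A separate simulation of the three-forest set-up gave 277 and 1,201 (6/6) and 255 and 1,104 (4/8) at 100 and 500 trees, inside these ranges. With 9 patients split 4/5, the counts were about 293, 1,347 and 2,499.

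**Step 3: why the count follows the trees.** With so few patients each tree makes about one split. At 4/8 there were 312, 1,584 and 3,164 splits for 300, 1,500 and 3,000 trees in total, falling on 300, 1,371 and 2,431 distinct features. MI adds little: 31% to 100% of noise features had MI > 0, depending on estimator and class split.

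**Step 4: does the cross-validation repair it?** Pairs of noise questions, 6/6, three forests of 100 trees, a small neural network, 5 folds, 11 runs. Features were kept on importance > 0 only.
- Selection on all patients before the folds, the order in 3.3.2: mean accuracy 1.00, minimum 1.00.
- Selection repeated inside each training fold: mean accuracy 0.52 (SD 0.13), which is chance.

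**Step 5: when is nothing returned?** Zero features were kept only when all patients fell in one class.

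**The case against.** The strongest counter-argument is that the zero cut-off is not the main source of a misleading result. Step 4 keeps uncalibrated features in both arms, yet nesting alone brings accuracy back to chance. This stands: the false accuracy comes from selecting before cross-validating, so nesting belongs in the fix. Nesting does not, however, change what the QMI rule returns. The list still consists of noise and is still labelled useful, and min-max scaling still produces a 0-100 ranking.

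The mechanism also depends on unstated choices. Permutation importance, another Preference-score formula or correlated features (3.3.2 says many are correlated) would change the counts. That is why a range is given.

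Three stronger readings are tempting, and the documents do not support them:

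- A reader might infer that the rule does not screen at all. It discards about 98.5% of features at 100 trees per forest and about 93% at 500. What it lacks is calibration.
- A reader might quote one count. Pooling all features into a single 500-tree forest gives about 406 to 479 with binned MI, but 3.3.2 specifies separate forests and the tree count is not stated.
- A reader might infer that a phenotype will always be found. A non-empty feature list is an input to the third step, not a phenotype, and neither 2.3.4 nor 9.5 defines identification.

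Finally, this is an exploratory aim, analysed descriptively, in a 12-patient pilot. That limits the consequences, but does not make an uncalibrated list informative.

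**Conclusion.** The concern holds in this form. Retention at QMI > 0 has no chance reference. With 12 patients, two classes and 20,000 noise features, it keeps roughly 225 to 2,430 features per question for 100 to 1,000 trees per forest, under the assumptions listed. A feature list and a question ranking are returned whenever both classes occur. The cross-validation as ordered in 3.3.2 does not expose this and can show perfect accuracy on noise. The primary feasibility endpoint and the secondary endpoints are not affected.

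**What to change.** In 3.3.2:

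1. Repeat feature selection inside each training fold.
2. State the tree count, importance type, Preference-score formula, MI estimator and the definition of the two classes.
3. Rerun the whole pipeline with outcome labels shuffled across patients, for example 200 times. Report the number of features retained and the cross-validated accuracy for real labels beside their shuffled-label distributions. Because many question pairs are tried, name one accuracy summary in advance and take the same summary from every shuffled run.
4. Call features kept by QMI > 0 candidates only. State that no behavioral phenotype was identified unless real-label accuracy exceeds the 95th percentile of the shuffled-label accuracies.

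A per-feature cut-off at the largest shuffled QMI should not be the rule. With 82 of 6,667 features tried per split, a given marker is tried at the first split of only about 500 × 82/6,667 = 6 of 500 trees, so its score is small and unstable. In two small runs with a planted perfect marker (6,667 features, 500 trees, 6/6, 40 shuffles), its QMI was 0.0042 and 0.0028 against cut-offs of 0.0097 and 0.0083. Nothing was retained there, or in three further planted-marker runs.

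The cost is computing time and a short text change, with no added patients or visits. The downside is that with 12 patients the likely result is that no phenotype is identified.

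### Storyline features are chosen with the outcome labels before the only cross-validation, so the returned accuracy is biased upward; the completion-rate interval also ignores clustering by patient

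*Combined protocol and SAP*

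**What the plan says.** Section 3.3.2 gives three ordered steps. Step 1 drops low-variance questions without using the labels. Step 2 multiplies a score from random forest importance by mutual information, giving QMI, and keeps features with QMI above zero. The labels drive this choice: "The usefulness of the features is determined from their ability to differentiate the two classes in a study, such as control versus sick patients". In step 3 "the input is all of the candidate questions and their optimized speech, vocal and facial features revealed from Short Story Score #2", and there "questions are tested in all possible pairwise combinations with 5-fold cross validation".

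Accuracy is a stated output: "The final results will return the ranking for each question and the mean classification accuracy values for each question". It also feeds the question score. "Each pairwise question combination is then assigned an index", with no rule for the index, and then "we multiply the index and the mean classification accuracy for all question pairings in which that question was included in the predictive model". After scaling to 0-100, "a low score indicates questions that can be pruned".

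Section 2.3.4 makes a behavioural phenotype that predicts response to ketamine an exploratory endpoint. No section defines the two classes for this single-arm trial.

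Section 2.3.5 sets a further exploratory endpoint as the share of questionnaires filled in. Section 9.5 attaches an exact binomial 95% interval to it and describes the exploratory analyses as descriptive.

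**The concern.** Cross-validation estimates performance on new patients only if the held-out patients played no part in building the model. Here their labels have already been used to pick features from a pool far larger than the 12 patients. The accuracy is then partly a measure of how well chance patterns were found, and it can look high when nothing is predictive. Because this accuracy is the only evaluation described for the phenotype endpoint, and because low-ranked questions can be dropped, a chance result could be carried forward as a finding.

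Two further problems sit alongside it. If the pair index is a running number, the question score depends on the order in which questions are listed. And an exact binomial interval assumes independent forms, whereas each patient supplies several, so the completion interval can be too narrow.

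**Working it through.** The documents state no expected accuracy, class split or completion rate, so there is no figure of theirs to reproduce.

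**Inputs from the documents.** 12 patients (9.1); more than 20,000 features per question, label-based selection with QMI > 0, a two-layer network and 5-fold cross-validation (3.3.2). Section 3.3.2 also says of the features that "many are correlated or not useful for detecting some phenotypes of interest", without a figure.

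**Assumptions.** Class splits 6/6, 8/4 and 9/3; feature correlation from none to strong; 200 trees; median-split mutual information; the intraclass correlation (ICC) of form completion.

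**Hand check of the mechanism.** With no signal and a 6/6 split, all C(12,6) = 924 label arrangements along a feature's ordering are equally likely, and 2 separate the classes perfectly. The expected number of perfectly separating noise features is 20,000 × 2/924 ≈ 43 per question. Selection finds them, and they also separate the held-out patients.

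**Null simulation.** Two questions × 20,000 features, labels unrelated to features, stratified 5-fold cross-validation, 80 runs per setting. Correlated features: X = √ρ·(latent factors × unit loadings) + √(1−ρ)·noise, where ρ is the shared variance. Un-nested means selection before cross-validation, as written; nested means selection repeated in each training fold.

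| Split | Features | Un-nested | Nested | Majority class |
|---|---|---|---|---|
| 6/6 | independent | 100% | 48% | 50% |
| 6/6 | 20 factors, ρ 50% | 99.7% | 51% | 50% |
| 6/6 | 10 factors, ρ 80% / 95% | 85% / 74% | 49% / 50% | 50% |
| 6/6 | 5 factors, ρ 80% / 95% | 77% / 61% | 52% / 49% | 50% |
| 6/6 | 3 factors, ρ 80% / 95% | 72% / 58% | 48% / 49% | 50% |
| 8/4 | independent | 100% | 52% | 67% |
| 8/4 | correlated | 62-74% | 51-54% | 67% |
| 9/3 | independent | 100% | 54% | 75% |
| 9/3 | correlated | 60-68% | 49-55% | 75% |

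Un-nested exceeded nested in all 23 settings, by 5 to 52 points. A different selector and classifier (standardized mean difference, nearest centroid; 6/6, 150 runs) gave the same direction: 1.00 against 0.44 (independent), 0.97 against 0.46 (10 factors, 80%) and 0.76 against 0.50 (3 factors, 95%).

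**Ranking.** Six questions, one informative, so chance of first place is 1/6 = 17%. Without any index, the informative question came first in 17% of un-nested runs against 79-100% nested when features were independent. With strongly correlated features it was 78-96% against 67-99%, and un-nested did better in two of four settings.

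**Pair index, if it is a running number.** Four questions, pairs numbered 1-6 in listing order, equal accuracy everywhere: index sums are 1+2+3 = 6, 1+4+5 = 10, 2+4+6 = 12 and 3+5+6 = 14. Min-max scaling gives 0, 50, 75 and 100 from listing order alone. With six questions, the first-listed one perfect in all its pairs and every other pair at 50%, it scores 1+2+3+4+5 = 15 while the others score 16 to 30, so the best question ranks last. In the ranking simulation such an index cut the nested first-place share from 67-100% to 32-68%.

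**Completion interval.** Forms per patient could be 4 (Storyline occasions in the Schedule of Events), 10 (seven 10-minute baseline parts plus 3 follow-ups) or 36 (EDS 8, QIDS 7, DADDS 7, FACIT-Sp 4, Storyline 4, MEQ 3, NADA 3). The design effect is 1 + (m−1)·ICC for m forms. At m = 4, ICC 0.3 and 36 of 48 forms complete, it is 1 + 3×0.3 = 1.9, so the effective n is 48/1.9 = 25.3; the exact interval widens from 60.4-86.4% to 53.9-89.9%. Coverage of the nominal 95% exact interval, beta-binomial with a true rate of 80%, 40,000 runs:

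| Forms per patient | ICC 0.1 | ICC 0.3 | ICC 0.5 |
|---|---|---|---|
| 4 | 92% | 85% | 78% |
| 10 | 86% | 71% | 61% |
| 36 | 67% | 45% | 35% |

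With 4 occasions and ICC 0.05, coverage is 94%; at a 95% completion rate it is 93-98%.

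**The case against.** The leak is an inference. Section 3.3.2 never states that step 2 uses every patient's labels; this follows from the order of steps and from silence on nesting, and one sentence confirming nested selection would remove the main point. That is fair, but the present text reads the other way.

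The section also sits in the background, reads like a generic platform description, and 9.5 lists no accuracy among its summaries. It is nonetheless the only method given for the 2.3.4 endpoint, and it names accuracy as an output. The undefined classes make the gap wider.

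On size, the 100% figures need independent features, which the plan itself says is not the case. The simulated forest ran on all features together rather than by speech, vocal and facial set. With 3 or 4 patients in the smaller class, some test folds contain none of them. All this stands: the direction is secure, the magnitude is not. Harm to the ranking is likewise not shown when features are strongly correlated.

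The index figures depend on a guess about an unstated rule. The completion point is mainly an undefined denominator: with one yes/no per patient the exact interval is right, and with 4 occasions and low ICC the error is small. The 36-form count is the least secure, since several appendix forms carry signature lines that suggest paper. These limits are accepted.

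**Conclusion.** The concern holds. Followed as written, 3.3.2 gives an upward-biased classification accuracy. With 12 patients and no signal the excess over nested accuracy was 5 to 52 points, reaching 100% apparent accuracy with independent features; where in that range the trial would fall depends on class split and feature correlation, neither of which is stated. Accuracy also needs a benchmark: at a 9/3 split, always predicting the larger class already gives 75%. Damage to the ranking is established only for independent features, or if the index is a running number.

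The completion interval can under-cover, from negligibly (4 forms, low ICC) to severely (36 forms), depending on the denominator and the assumed ICC. The completion point estimate is unaffected.

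Both endpoints are exploratory and the primary feasibility conclusion does not change. The plan should be corrected before analysis. Confidence is medium, because the size is unknown and nesting may have been intended but not written.

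**What to change.** In 3.3.2 and 9.5, for the algorithm:

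- Define the two classes for this trial.
- Repeat all label-based selection inside each training fold, and keep all of a patient's recordings in one fold.
- Take both accuracy and ranking from that nested procedure, so that no question is scored on a leaked accuracy. Show the results beside the majority-class rate and the same full procedure run on permuted labels. Alternatively, do not report accuracy as performance at n = 12.
- State what the pair index is, and do not weight by a running number. The mean nested accuracy over the pairs that contain a question would serve.

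In 9.5, for completion:

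- State the denominator, and whether forms due after withdrawal or death count.
- Report the questionnaire percentage with a per-patient median and range, without a pooled binomial interval.
- Keep the exact interval for one yes/no per enrolled patient, such as completing every Storyline assessment due. It covered 96-99.5% in all 36 settings tried. A patient-level t interval fell to 68-72% at a 95% rate and ICC 0.5, so it is not proposed; a cluster bootstrap was not tested.

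The cost is analysis code and a few sentences, with no new data. Selection is fitted about five times as often, again for each permutation, and the reported accuracy will be lower. The patient-level interval is wider: on average 38-56 points with 4 occasions (9 of 12 gives 42.8-94.5%) against 13-24 for the pooled one. It describes patients who complete everything, so the share of forms is left without an interval.
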